7.1.1 Imaging Guidelines

In accordance with protocol guidelines for imaging, each study center will follow standard practice for (transthoracic) echocardiographic imaging and subject preparation. This includes subject positioning and comfort measures, pre- and post-dosing.

Refer to [Image Evaluation Guidelines](#) for details.

The 2008 American Society of Echocardiography consensus statement on contrast agents in echocardiography advocates a team approach for the successful introduction and implementation of contrast protocols into an echocardiography laboratory.⁴ The team would primarily consist of the sonographer, physician echocardiographer, and where available, nursing staff who are competent and certified in obtaining IV access and administration of IV agents.

It is recommended that the sonographers be appropriately qualified and credentialed in echocardiography and the responsible investigators be independent and competent echocardiographers with skills in basic and advanced life support.

Each subject will undergo an unenhanced ultrasound examination. After unenhanced imaging, subjects will then receive 1 dose of NH002 at the assigned cohort dose level. Before contrast administration, the instrument settings on the ultrasound imaging system, including gain, MI,

[figure not shown]
focal depth, time gain compensation, and dynamic range will be optimized for each subject and kept constant during the imaging.

For each dose, two-dimensional transthoracic echocardiography will be performed using both B-mode ultrasonography and contrast-specific ultrasonography before agent administration and using only contrast-specific ultrasonography after agent administration. The pre-injection imaging will be performed once in both apical 4- and 2-chamber views, first using B-mode ultrasonography and then contrast-specific ultrasonography. Switch between both apical views or imaging modes will be performed in 30-second intervals. Upon NH002 administration, the post-injection imaging will be subsequently performed in both apical 4- and 2-chamber views using only contrast-specific ultrasonography. During this period, alternation of both apical views will be performed in 30-seconds until 10 minutes after NH002 administration. In both imaging sessions, the 4-chamber view will be performed first.

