DICOM cineloop sequences will be stored. Each cineloop sequence will be acquired for a duration of 5 seconds whenever the imaging mode or the imaging view is changed. [REDACTED]

[See Figure 5](#) for details.

Figure 5: Imaging Guidelines

Each subject should have 24 DICOM file(s) for the NH002 dosing and the unenhanced imaging. These files will be exported to the USB flash drive or CD from the ultrasound machine.

The video for NH002 dosing will be recorded by an external video recorder in mp4 format. The sponsor will provide each site with a recording instrument confirmed to be compatible with [REDACTED]. All clinical sites will use the same model of the recording instruments. The recording duration will be at least 15 minutes for each dosing period (starting from approximately 5 minutes before

and continuing until 10 minutes after dosing). Each subject should have at least 1 video file stored in a USB flash drive or CD (for the NH002 dosing and the unenhanced ultrasound imaging). The sponsor will also provide USB flash drives or CDs to sites.

Central image evaluations will occur offsite to ensure that the blinded reader(s) perform their image evaluations independently. The blinded central reader(s) will not have any knowledge of subject identifiers nor dose level received to obtain an image. DICOM image groups obtained in each subject will be merged and presented to the blinded reader(s) in a random sequence. Each blinded evaluation will be locked in the dataset shortly after it is obtained and before additional types of image evaluations are performed, if indicated *and applicable*.

If indicated *and applicable*, consensus image evaluations (or consensus reads) can be performed after the individual readings (if applicable) are completed and locked. (These consensus reads will NOT serve as the primary image evaluation used to demonstrate any preliminary efficacy of NH002.) **If used**, the consensus reads will also be locked once obtained and before additional types of blinded readings are performed.

The blinded central reviewer(s) with appropriate training, education, and qualifications will assess the echocardiographic images for this study. The blinded central reader(s) will be provided with redacted USB flash drive(s) or CD(s) in order to access and score randomized video image groups without knowledge/information of dosing or subject identifiers. Refer to [Image Evaluation Guidelines](#) for more information.

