8.2.1.3 Dosing

After all procedures have been performed, NH002 will be administered. Each subject will receive an assignment to 1 of the 3 NH002 dose levels (2.5 µl/kg, 5.0 µl/kg, or 10.0 µl/kg IV bolus). See [Section 7.5.1](#) for details. The following procedures will be performed after the contrast injection:

- Imaging should proceed as specified in [Section 7.1.1](#).
- Modified 12-lead ECG monitoring to continue until completion of imaging (ie, to 10-minutes after dosing). Any clinically significant ECG changes indicative of arrhythmia or S-T segment change identified after dosing from the modified 12-lead ECG monitoring will be recorded in a timely manner, and a standard 12-lead ECG will be conducted subsequently (when the first recorded ECG change occurs). The imaging will be temporarily stopped for the conditionally triggered standard 12-lead ECG examination. The results of the modified 12-lead ECG will also be included into the subject's study file as reference. See [Section 9.1.2.2.7](#).
- Pulse oximetry: SpO₂ should also be measured and recorded until completion of imaging (ie, 10 minutes after dosing).
- VS: BP, body temperature, HR, and RR should be measured and recorded until completion of imaging (ie, 10 minutes after dosing).
- Record any AEs that may occur and any changes in concomitant medication.

8.2.1.4 10 Minutes After Dosing

The following procedures will be performed approximately **10 minutes after** the contrast injection:

- VS: Measurements include BP, body temperature, HR, and RR
- Modified 12-lead ECG monitoring to continue until completion of imaging (ie, to 10-minutes post dosing); See [Section 9.1.2.2.7](#).

- Standard 12-lead ECG. Site(s) should make every effort to target the timing to be as close to the end of the modified 12-lead ECG monitoring (10 minutes after dosing) as possible.
- Pulse oximetry: SpO₂
- Imaging should proceed as specified in [Section 7.1.1](#).
- Record any AEs that have occurred since the previous visit and any changes in concomitant medication.

8.2.1.5 30 Minutes After Dosing

The following procedures will be performed approximately **30 minutes after** the contrast injection (+5 minutes):

- VS: Measurements include BP, body temperature, HR, and RR
- Standard 12-lead ECG
- Focused PE: A focused PE will include cardiopulmonary (observation, palpation, percussion, auscultation) and skin (turgor, pallor, cyanosis, erythema, lesions) assessments.
- Pulse oximetry: SpO₂

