16 APPENDICES

16.1 Image Evaluation Guidelines

Sponsor-recommended equipment/platforms:*

| | |
|----------------------------|-----------------------------------|
| Ultrasound System | [REDACTED] with contrast LVO mode |
| Video Recording Instrument | [REDACTED] |
| Image Evaluation Software | Windows Media Player/DICOM viewer |

**Equipment other than the listed can be used after discussion and approval by the sponsor.*

Equipment technical settings to be used at each site: Site should follow standard institutional guideline(s) for equipment technical settings and subject preparation, positioning, and overall comfort measures.

Site qualification process: Local site imaging technicians must be trained and qualified in equipment operation, including the ability to identify faulty or unacceptable images and understand the importance of repeating imaging when appropriate. (In the event of faulty or unacceptable images, an unscheduled visit can be scheduled to repeat all necessary procedures.)

Acquisition quality control monitoring process:

A checklist will be used for quality control. Checklist for each treatment:

- Subject ID and treatment number were input correctly on ultrasound imaging system and external video recorder
- Investigator confirmed settings of mechanical index, depth, focal depth, dynamic range, gain, and time gain compensation were optimized for each subject
- 4-chamber view of pre-injection B mode acquired
- 2-chamber view of pre-injection B mode acquired
- 4-chamber view of pre-injection contrast mode acquired
- 2-chamber view of pre-injection contrast mode acquired
- Treatment administered
- 4-chamber view of post-injection contrast mode acquired
- 2-chamber view of post-injection contrast mode acquired
- 19 transitions between 2-chamber and 4-chamber view post-injection. Two or less transitions may be skipped when a standard 12-lead ECG is conditionally triggered during the imaging session.
- A video containing consecutive pre-injection and 10-minute post-injection sessions acquired
- 4 pre-injection DICOM cineloop sequences acquired
- 20 post-injection DICOM cineloop sequences acquired (including 10 DICOM cineloop sequences of 4-chamber view and 10 DICOM cineloop sequences of 2-chamber view). Two or less sequences may be skipped when a standard 12-lead ECG is conditionally triggered during the imaging session.)

[figure not shown]
Data storage and transfer:

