USB flash disks or CD(s) labeled with subject ID will be used to store and transfer video files and DICOM files acquired in the study. Each subject's image data will be stored in one USB flash disk or CD(s) and shipped to the sponsor or designated contract research organization for randomized sequencing (for central blinded reviews).

Standards for Image Evaluation:**(a) LVO:**

- 0 = none (no visible contrast within the LV cavity);
- 1 = faint (weak or trace effect of contrast within the LV cavity);
- 2 = moderate (some areas of the LV cavity fully opacified but without a time when the whole cavity was filled with contrast to the same high density);
- 3 = complete (homogeneous and high intensity effect).

(b) LVEBD: The apical 4-chamber and 2-chamber views of the left ventricle were divided into segments by using cardiac maps. A total delineation score (0-24) was obtained by adding the scores (0 = inadequate, ie, border not visible; +1 = sufficient, ie, border barely visible; +2 = good, ie, border clearly visible) from the six individual segments in each of the two views.

- 0 = inadequate, ie, border not visible;
- 1 = sufficient, ie, border barely visible;
- 2 = good, ie, border clearly visible.

Image display sequence and randomization.

The sponsor or designated contract research organization will merge the grouped images obtained in the study from each subject and present the merged set to the blinded reader in a random sequence. The whole recorded image data will be used for scoring by the blinded reader(s). The blinded reader(s) should document the time points of the best images used for LVEBD scoring as well as the start and end time points of useful contrast imaging.

Central blinded reader training and qualification:

Central blinded reader(s) have been selected to assess the echocardiographic images for this study because of their background training and qualifications. These selected blinded central reader(s) will also be trained in scoring procedures for LVO and LVEBD using sample images, prior to the central image evaluations.

Timing of image reads and the read process:

Merged/randomized image scoring of blinded central reader(s) will be done after all the images in the study are obtained.

Imaging data lock process:

Each blinded evaluation will be locked in the dataset shortly after it is obtained and before additional types of image evaluations are performed.

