5.4. Secondary Endpoints Analysis

5.4.1. Secondary Efficacy Endpoints

5.4.1.1. Definition of endpoints

- The percentage of subjects with moderate or complete LVO, defined by an LVO grade of 2 (moderate) or 3 (complete), as assessed by the blinded central reader(s);
- The percentage of subjects with complete LVO, defined by an LVO grade of 3 (complete), as assessed by the blinded central reader(s);
- The change from baseline on the LVEBD score, defined using a standard 12-segment model, as assessed by the blinded central reader(s). The LV endocardium of the 4- or 2-chamber apical views are divided into 6 segments, with 2 basal, mid-, and apical segments in each view. For each segment, LVEBD is graded as follows: 0 = inadequate border (border not visible); 1 = sufficient (border barely visible); 2 = good (border clearly visible). A total delineation score (0-24) is obtained by adding the scores from the 6 individual segments in each of the 2 views.
- The changes from baseline on LVEBD score of subjects with suboptimal LVEBD at baseline, as defined by 2 or more contiguous segments of 6 segments that cannot be

visualized reliably in either the apical 4- and/or the 2-chamber view, as assessed by the blinded central reader(s);

- The duration of clinically useful contrast calculated by measuring the time between the disappearance of shadowing effect (useful effect starts) and the time when moderate or full LV enhancement and contrast enhancement are no longer adequate (useful effect ends), as assessed by the blinded central reader(s).

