- Table 13.1.2.1: Summary of LVEBD Score, Per Protocol Set
- Figure 13.1.2.2: LVEBD Score, Per Protocol Set
- Figure 13.1.2.3: Change of LVEBD Score, Per Protocol Set
- Table 13.2.1.1: Summary of LVEBD Score for Subjects with Suboptimal LVEBD at Baseline (as defined by 2 or more contiguous segments of 6 segments that cannot be visualized reliably in either the apical 4- and/or the 2-chamber view), Full Analysis Set
- Figure 13.2.1.2: LVEBD Score for Subjects with Suboptimal LVEBD at Baseline (as defined by 2 or more contiguous segments of 6 segments that cannot be visualized reliably in either the apical 4- and/or the 2-chamber view), Full Analysis Set
- Figure 13.2.1.3: LVEBD Score for Subjects with Suboptimal LVEBD at Baseline (as defined by 2 or more contiguous segments of 6 segments that cannot be visualized reliably in either the apical 4- and/or the 2-chamber view), Full Analysis Set
- Table 13.2.2.1: Summary of LVEBD Score for Subjects with Suboptimal LVEBD at Baseline (as defined by 2 or more contiguous segments of 6 segments that cannot be visualized reliably in either the apical 4- and/or the 2-chamber view), Per Protocol Set
- Figure 13.2.2.2: LVEBD Score for Subjects with Suboptimal LVEBD at Baseline (as defined by 2 or more contiguous segments of 6 segments that cannot be visualized reliably in either the apical 4- and/or the 2-chamber view), Per Protocol Set
- Figure 13.2.2.3: LVEBD Score for Subjects with Suboptimal LVEBD at Baseline (as defined by 2 or more contiguous segments of 6 segments that cannot be visualized reliably in either the apical 4- and/or the 2-chamber view), Per Protocol Set
- Listing 06.2: Image Evaluation - LVEBD Score, Safety Set
- Duration of Clinically Useful Contrast Enhancement

The duration of clinically useful contrast enhancement is the number of minutes between start time point and end time point of useful contrast imaging, rounded to one decimal place.

The formula for duration calculation is as below.

Duration (Minutes)=(End Time (hh:mm:ss) of Useful Contrast Imaging - Start Time (hh:mm:ss) of Useful Contrast Imaging)/60, rounded to one decimal place.

The descriptive statistics (n, mean, standard deviation, median, minimum, maximum, and 95% CI) of the duration of clinically useful contrast enhancement will be presented by each dose group and overall. The unit of duration is minute.

Furthermore, the boxplots of duration of clinically useful contrast enhancement will be presented by each cohort and overall.

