5.7. Handling of Missing Data

As all treatments are scheduled in a single study visit, the level of missing data for the primary endpoint is anticipated to be small. Every attempt will be made to avoid missing data. All subjects will be used in the safety analysis, using non-missing data available. No imputation process will be used to estimate/substitute missing data.

6. References

1. Protocol Deviation Handling Plan (PDHP) Version 1.0.
2. The Dose Escalation Committee Charter Version 1.0.
3. NH002-LV_Protocol_v1.0.
4. Data Transfer Specification TRUS-10006193, ECHO Final 3.0, 16 Sep 2020.
5. Specification of Suboptimal Echocardiogram Data Transfer_20201116_TRUST.

7. Appendices

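### Duration of useful contrast is analysed as if every end were observed, although planned imaging stops 10 minutes after injection; the SAP has no rule for an end not yet reached and no label for subjects who never reach useful contrast

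*SAP*

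**What the plan says.** **Endpoint.** SAP 5.4.1.1 starts the interval when shadowing disappears and closes it at "the time when moderate or full LV enhancement and contrast enhancement are no longer adequate (useful effect ends". The end is therefore an event that has to be seen on the images.

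**Calculation.** SAP 5.4.1.2 says: "The duration of clinically useful contrast enhancement is the number of minutes between start time point and end time point of useful contrast imaging". It plans n, mean, SD, median, minimum, maximum and 95% CI by dose and overall, with boxplots, in the Full Analysis Set and the Per Protocol Set.

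**Imaging window.** Protocol 7.1.1 says that "alternation of both apical views will be performed in 30-seconds until 10 minutes after NH002 administration". Protocol 8.2.1.3 runs monitoring "until completion of imaging (ie, to 10-minutes after dosing". The checklist in Protocol 16.1 has "A video containing consecutive pre-injection and 10-minute post-injection sessions acquired". On the video, Protocol 7.1.1 says: "The recording duration will be at least 15 minutes for each dosing period", from about 5 minutes before dosing to 10 minutes after it.

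**Reader instruction.** Protocol 16.1 asks readers to document the times of the best images "as well as the start and end time points of useful contrast imaging". It does not cover enhancement that is still adequate at the last frame or never becomes adequate.

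**Missing data.** SAP 5.7: "No imputation process will be used to estimate/substitute missing data".

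**The concern.** Two predictable cases have no stated rule.

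- *The end has not occurred when imaging stops.* The true duration is then known only to exceed the observed one. An ordinary mean and CI treat the value as complete or lose it. The bias falls on the doses whose contrast lasts longest. Protocol 5.2 expects a longer half-life than that of approved agents, so the case is not far-fetched.
- *Useful contrast never starts.* There is then no start and no end, and with no imputation the subject appears to have no duration. The mean describes those who reached useful contrast, but is not labelled so. Protocol 7.1 and 7.5.1.2 foresee subjects with no visible contrast effect.

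The first gap pulls long-lasting doses down. The second makes weak doses look better than they would over all dosed subjects. Together they tend to shrink the differences between doses, which are what this endpoint is meant to describe.

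**Working it through.** **1. Is 10 minutes really the planned limit?** Alternating views every 30 seconds for 10 minutes gives 600/30 = 20 cineloops and 19 transitions. With 4 pre-injection loops that is 24 files, and 5 + 10 = 15 minutes of video. All four figures match Protocol 7.1.1 and 16.1.

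**2. Ceiling.** Largest reportable duration = 10 − start. For assumed starts of 1, 2 or 3 minutes it is 9, 8 or 7 minutes.

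**3. Effect of the ceiling on the mean.** The documents give no duration that can be used: the imaging lifetime in Protocol 5.2.2 is redacted. What follows is illustration only. Assume gamma durations with mean m and SD s, so shape a = (m/s)² and scale s²/m, and a window W. Let F be the distribution function at W with shape a, and F1 the same with shape a + 1.

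- Share cut off = 1 − F
- Mean if the last frame is entered = m·F1 + W·(1 − F)
- Mean if the end is left blank = m·F1/F

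Example: m = 8, s = 3, W = 9 gives F = 0.672 and F1 = 0.531. Entered: 8 × 0.531 + 9 × 0.328 = 7.20. Blank: 8 × 0.531/0.672 = 6.33 (from unrounded values).

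| True mean (SD) | W | Cut off | Mean, entered | Mean, blank |
|---|---|---|---|---|
| 3 (1.5) | 9 | 0.2% | 3.00 | 2.98 |
| 6 (2) | 9 | 8% | 5.90 | 5.63 |
| 6 (2) | 8 | 16% | 5.79 | 5.38 |
| 6 (2) | 7 | 28% | 5.57 | 5.02 |
| 8 (3) | 9 | 33% | 7.20 | 6.33 |

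**4. Effect on the 95% CI.** Coverage of the true mean by a t interval (assumed; the SAP names no method), n = 12, W = 9, 200,000 simulated groups:

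| True mean (SD) | Complete data | Entered | Blank |
|---|---|---|---|
| 3 (1.5) | 94% | 94% | 94% |
| 6 (2) | 94% | 94% | 89% |
| 8 (3) | 94% | 79% | 31% |

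**5. Effect on the median.** For mean 8, SD 3, W = 9, the average sample median is 7.61 if the last frame is entered, against 7.68 with complete data; it changes in 17% of groups. If the end is left blank, the median is that of durations up to 9 minutes, which is the gamma quantile at F/2 = 0.336: 6.46, against a true 7.63.

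**6. A different shape.** Lognormal durations with log-SD 0.4 and a start at 1 minute give the same picture with the last frame entered. True median 3: under 1% cut off. Median 8: 38% cut off, mean 7.43 against 8.67. Median 12: 76% cut off, mean 8.58 against 13.00; more than half are cut off, so the observed median is also held at 9.0.

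**7. Subjects who never reach useful contrast.** With k such subjects among 12, the mean among reachers is 12/(12 − k) times the mean with zeros: 1.09, 1.20, 1.33 and 1.50 for k = 1 to 4. For an assumed mean of 5.0 minutes among reachers, the means with zeros for k = 1, 2 and 4 are 5 × 11/12 = 4.58, 5 × 10/12 = 4.17 and 5 × 8/12 = 3.33.

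**The case against.** **The SAP already plans a median, a maximum and boxplots.** This stands in part. If the last frame is entered, the median is robust until half of a group is cut off, and the boxplots would hint at values piling up near the ceiling. It does not help the mean and its CI, or the median if ends are left blank. Nothing planned counts the cut-off ends.

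**A reader might infer that subjects without useful contrast vanish uncounted.** The documents do not support that. The duration table gives n, SAP 5.2.1 reports the size of each analysis set, Table 12.1.1 counts every LVO grade, and Listing 06.3 shows individual data. That they drop out is itself inferred from the formula and the no-imputation rule; a reader could record equal start and end times. What remains is narrower: a shortfall in n does not separate never reached from missing or unreadable, and the LVO table is not an exact match, because a grade 2 subject could still have no useful interval.

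**A reader might infer that the bias is large, or that it affects escalation.** Neither can be shown. The 31% coverage needs both the longest durations in that table and blank ends. Central reads follow the end of all imaging (Protocol 16.1), so escalation does not use them. The dose-selection rules in Protocol 10.6 cite efficacy only in general, and the one utility named in Protocol 7.3.1 is LVO.

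**The minimum video length might suggest a later or varying cut-off.** A longer recording is allowed, but no imaging beyond 10 minutes is planned.

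**A rule may exist elsewhere.** SAP 7.2.2 refers to a Data Transfer Specification for these reads, which was not available here. It may code both cases; the SAP itself states nothing.

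**Conclusion.** The point holds, within limits. The endpoint closes on an event, the planned window closes at 10 minutes, and the SAP analyses end minus start as complete. Any subject still adequately enhanced at the last frame lowers that dose's mean under either coding, and the CI does not reflect it. The direction follows from the text; the size does not. It is negligible if durations are short (true mean 3 minutes) and about 0.8 to 1.7 minutes in the longest gamma case (8 − 7.20 and 8 − 6.33), under assumed distributions and an assumed start at 1 minute. The median is a lesser concern, provided that the last frame is entered and fewer than half of a group are cut off.

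The gap for subjects who never reach useful contrast is one of labelling and cause. A summary among reachers is a legitimate quantity if it is named as such.

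The endpoint is secondary and descriptive, and the SAP has no hypotheses, so no test or power is affected. The gap is still worth closing: without a count of cut-off ends, readers of Table 14.1.1 cannot tell which situation they are in.

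**What to change.** In SAP 5.4.1.2:

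- **Cut-off ends.** When enhancement is still adequate at the last frame, record the last imaged time as the end, flag it as censored in the central-read data, and report the number flagged by dose.
- **Main summary.** Pre-specify a Kaplan-Meier median with 95% CI for all dose groups, whether or not censoring occurs, so that the method does not depend on the data. With no censoring it equals the ordinary median, apart from the convention for even numbers. Label any mean as restricted to the 10-minute imaging window.
- **Subjects who never reach useful contrast.** Report n/N reaching it by dose, separately from missing or unreadable images. Label the duration summary as among those reaching it, and give a summary with the others at 0 minutes as supportive.
- **Existing rule.** If the Data Transfer Specification already codes these cases, cite it and repeat its rule in the SAP.

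**Cost.** SAP wording and one extra field in the transfer, from existing recordings. If reads are already locked, end times must be checked against the end of each recording instead. A median may be reported as not reached if half or more of a group is censored. Kaplan-Meier also assumes that the available window (10 minutes minus start) is unrelated to duration; the flagged counts show how much rests on that. If no end is cut off and every subject reaches useful contrast, the results stay the same apart from that median convention, and the report can say so.
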